Patients undergoing surgical procedures requiring general anesthesia will first be approached for participation during the patient's preoperative visit, at the preoperative ENT clinic visit or on the day of surgery. A clinical research coordinator or other research personnel will be available to answer questions and obtain informed consent from the patient. It will be made clear to the patient that study participation is optional and that they can "opt out" at any time even if they have signed a consent form. In order to assure that our study participants are capable of understanding the information provided in the informed consent a single question screen will be used to detect inadequate health literacy: "How confident are you filling out medical forms by yourself?". This has been used in previous hospitals to detect poor health literacy [20]).

We intend on enrolling up to 100 male and female patients that meet eligibility criteria in order to have 60 patients who complete all study assessments. In addition to examining the potential effects of age, anesthetic drugs, and other patient and clinical factors on cognitive trajectories post-anesthesia, gender will be recorded and statistically examined as a potential contributor to different EEG patterns among our patients in this observational study.

8. Procedures:

- Upon enrollment, demographic data and medical history will be collected, subjects will be questioned about obstructive sleep apnea (OSA) using the STOP-Bang Questionnaire [21]). They will also be screened for cognitive impairment using Mini-Cog, Mini-Mental Status Examination (MMSE) and the Cognitive Failure Questionnaire (CFQ). A baseline pain assessment will be performed using the Visual Analog Scale. A baseline assessment of delirium will be obtained using the Confusion Assessment Method for Intensive Care Unit (CAM-ICU) criteria.
- Patients will be randomized to one of three groups on the morning of surgery by the Investigational Drug Service, before they enter the operating room. A randomization table will be provided and the subject assignment will be the next available number on the list. The study staff will be blinded to the list and the assignment. Group 1 will be given 0.5mg/kg of ketamine pre-incision as an intravenous (IV) bolus. Group 2 will receive 1.0mg/kg of ketamine pre-incision as

an IV bolus. Group 3. Will be administered saline/ placebo pre-incision an IV bolus. The provider will be blinded to the treatment assignment.

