This monitoring plan is appropriate, since ketamine, an anesthetic drug, has an excellent safety profile and is commonly used in anesthetic practice. In addition, the doses used in this study are unlikely to cause major or minor side effects (e.g., emergence reactions, hallucinations).

10. Statistical analysis

a. Sample size:

It was assumed about 30% delirium incidence in our population by standard care [1] [2] [3].

Estimating 5-8 oropharyngeal cancer surgeries per week with a conservative enrollment rate of 50%, we will be able to recruit 130-208 patients in 12 months. We plan to enroll about 85 eligible patients in order to achieve 20 completed patients in each randomized group. For this pilot study, with this sample size we will have 85% statistical power under significant level of 0.05 to detect delirium incidence rate drop at least 30% (placebo) to 5% (two treatment arms combined) by one-sized Mantel Haenszel test, and such effect size is supported by an existing trial [13].

b. Data analysis:

For primary aim, the incidence of delirium will be calculated in each of three randomized group with 95% confidence interval (CI), and compared between each ketamine treated group with placebo group through Fisher's exact test. For secondary aims, the dose response effect of ketamine on delirium reduction will be tested by Cochran-Armitage trend test. For other outcomes, such as pain (and/or change from baseline), MMSE (and/or change from baseline), EEG data, length of stay (LOS), and use of narcotics will be first described by summary statistics (mean, median, standard deviation, frequency, and etc.) by three randomized groups and then compared by Chi-square test/Fisher's exact test, ANOVA, or Krusal-Wallis test wherever appropriate. The analysis will be

conducted by the Biostatistics and Bioinformatics Shared Resource at Winship Cancer Institute.

The Winship OnCore system will be used for data entry and analysis.

11. Confidentiality

The privacy of the research subjects will be ensured through standard procedures for securing research data. Whenever possible, a study number, rather than a name, will be used on study records. Identifying information will not appear when we present or publish the study results. All interactions with subjects during the study will occur in a private setting. Only Emory owned computers will be utilized to store data with any identifiers and these are compliant with the Emory disc encryption policy.

12. Literature:

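### Fisher's exact test at 20 vs 20 uses only about half of its nominal 5%; Boschloo's exact test with Holm over the two doses would recover a modest amount of power for one sentence in section 10b

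*Combined protocol and SAP*

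**What the plan says.** Section 10b (Data analysis) makes the primary analysis pairwise: delirium incidence is "compared between each ketamine treated group with placebo group through" Fisher's exact test. It also plans a 95% CI for the incidence within each arm. It gives no sidedness, significance level or multiplicity rule for the two comparisons, and no interval for a difference between arms.

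Section 10a (Sample size) enrols patients "in order to achieve 20 completed patients in each randomized group", and section 8 has three randomised groups. The assumptions in 10a are a standard-care incidence of about 30% and a fall described as "30% (placebo) to 5% (two treatment arms combined". It states that "we will have 85% statistical power under significant level of 0.05", using a one-sided Mantel-Haenszel test (the word is misprinted). That is the only statement of sidedness in the document. No power is given for the pairwise Fisher tests.

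**The concern.** Fisher's test conditions on the total number of events. With 20 patients per arm and few events, only a handful of p-values can occur, so the test usually stops well short of 5%. An exact unconditional test is not tied to the observed total and can use more of the allowance while still guaranteeing the error rate. Boschloo's test takes the Fisher p-value as its statistic, so it rejects whenever Fisher does and sometimes when Fisher does not.

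At stake is some power in a 60-patient pilot, obtainable without recruiting anyone. Because there are two comparisons with one placebo group, the gain has to be judged after the family-wise error is controlled and not one comparison at a time.

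**Working it through.** **Inputs.** 20 completed per arm, alpha 0.05 and placebo 30% (section 10a); three groups (section 8). A rate of 5% in each ketamine arm is an assumption, since 10a gives 5% for the arms combined. Sidedness is unstated in 10b, so both cases are shown.

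**1. The plan's own figure.** With a placebo events and m events in total, 20 vs 40, the Mantel-Haenszel statistic is z = (a − 20m/60) / √[20·40·m(60 − m)/(60²·59)]. Summing binomial probabilities at 30% and 5% over all tables with z ≥ 1.645 gives 84.8%, which reproduces the stated 85%. That figure belongs to the pooled one-sided contrast and not to the tests in 10b.

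**2. Size of Fisher at 20 vs 20.** Size = maximum over a common rate p of Σ b(x₀;20,p)·b(x₁;20,p) over the tables with Fisher p ≤ 0.05, taken over all 21 × 21 tables. Result: 0.0253 two-sided, 0.0266 one-sided.

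**3. Boschloo, one comparison.** The p-value is the maximum over p of P(Fisher p ≤ observed Fisher p). Maximum size is 0.0464 two-sided and 0.043 one-sided. At 30% vs 5%, power goes from 44.6% to about 54% two-sided, and from 54.4% to about 63% one-sided.

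**4. Two comparisons sharing placebo.** Maximum family-wise error, two-sided:
- Fisher at 0.05 each, unadjusted: 4.7%
- Boschloo at 0.05 each, unadjusted: 8.4%
- Boschloo with Holm: 4.6%

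The full gain in step 3 is therefore not available; Holm is needed.

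**5. Power with both doses at 5% and placebo at 30%.**

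| | Given dose | Both doses | At least one dose |
|---|---|---|---|
| Fisher unadjusted, two-sided | 44.6% | 30.1% | 59.0% |
| Boschloo-Holm, two-sided | 49.1% | 39.2% | 59.0% |
| Fisher unadjusted, one-sided | 54.4% | 42.5% | 66.3% |
| Boschloo-Holm, one-sided | 57.3% | 48.3% | 66.3% |

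Check: with equal doses, given-dose power is the mean of the other two columns, e.g. (59.0 + 39.2)/2 = 49.1.

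At-least-one-dose power does not move because Holm's first step is at 0.025, where Boschloo rejects nearly the same tables as Fisher at 0.05. Against 0, 1, 2 or 3 ketamine events, both need 5, 7, 9 or 10 placebo events (two-sided). The gain arises at the second step, when one dose has already been declared.

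**6. Unequal doses.** With one dose at 5%, its two-sided power is 45.4% (Fisher 44.6%) if the other dose is at 15%, and 44.6% under either procedure if the other dose is at 30%, i.e. inert.

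**7. The table 6/20 vs 1/20.** Fisher one-sided p = [C(20,6)·C(20,1) + C(20,7)]/C(40,7) = (775,200 + 77,520)/18,643,560 = 0.0457; by symmetry the two-sided p is 0.0915. Boschloo two-sided p = 0.0464. If both doses show this table, the Holm-adjusted p is 2 × 0.0464 = 0.093. One-sided, Boschloo p = 0.023 and the adjusted p is 0.046. For the contrast that 10a actually plans, 6/20 vs 2/40, two-sided Fisher p = 0.013.

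**8. Effect estimate.** At 6/20 vs 1/20 the risk difference is −25 points. The Wilson limits are 14.5% to 51.9% and 0.9% to 23.6%. Newcombe's lower limit is −25 − √[(5 − 0.9)² + (51.9 − 30)²] = −47, and the upper is −25 + √[(23.6 − 5)² + (30 − 14.5)²] = −1. The within-arm intervals (12–54% and 0.1–25% if Clopper-Pearson; 10b names no method) overlap and do not describe the difference.

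**The case against.** The strongest reply is that Fisher is valid, familiar and standard for small 2×2 tables, and that its conservatism is doing useful work here: two unadjusted Fisher tests already hold the family-wise error at or below 4.7%, although 10b has no multiplicity rule. That stands. It is why the gain for a given dose is 4.5 points (49.1 − 44.6) and not the roughly 10 points seen in a single comparison. It also stands that section 4 expects the higher dose to work better, and step 6 shows that the gain shrinks to under 1 point or to nothing when the doses differ enough.

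The reply does not remove the point. In every scenario examined, power for the effective dose is at least that of the present plan, to the precision shown, and the chance of showing both doses effective rises clearly when both work. If Holm were added to Fisher instead, two-sided given-dose power would fall to 33.9%.

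A reader might infer that the planned result would miss significance because of Fisher, taking 6/20 vs 1/20 and p = 0.09. The documents do not support this. Section 10b never says two-sided; at the one-sided 0.05 used in 10a the same table gives p = 0.046. The 5% is planned for the combined arms, so 1/20 per arm is an inference. And if both doses show that table, two-sided Boschloo-Holm also misses 0.05, with adjusted p = 0.093.

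**Conclusion.** This is a cheap improvement in efficiency; the planned test is not wrong. Fisher at 20 vs 20 spends about half of its nominal 5% whichever sidedness is meant. Boschloo with Holm converts part of the unused allowance into power: 4.5 points for a given dose and 9.1 points for both doses two-sided (2.9 and 5.8 points one-sided), with no change in the chance of showing at least one dose effective.

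These figures assume exactly 20 analysed per arm, placebo at 30% and both doses at 5%. The gain for a given dose largely disappears if only one dose works.

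It would also go too far to infer that low power comes from the choice of test and not from the number of patients. Even Boschloo without adjustment reaches only about 54% two-sided, or 63% one-sided, per comparison. Most of the distance to 85% comes from comparing 20 with 20, whereas 10a powered a pooled contrast of 20 with 40. A change of exact test does not close that gap.

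**What to change.** Amend section 10b as follows:
- State the sidedness and the significance level of the primary comparisons.
- Replace Fisher's test for the two dose-placebo comparisons by Boschloo's exact unconditional test, with Holm's step-down over the two doses at an overall 0.05.
- Report each dose-placebo risk difference with a 95% CI (Newcombe or Miettinen-Nurminen) beside the within-arm intervals. Say that these intervals are not adjusted for multiplicity: at 6/20 vs 1/20 in both doses the Newcombe interval just excludes zero while the two-sided Holm-adjusted p is 0.093.

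The cost is a short text change and standard software, with no extra patients or data. There are two drawbacks. Boschloo's test is less familiar to readers than Fisher's. It must also not be used at 0.05 for each dose without Holm, since the family-wise error could then reach 8.4%. The sidedness and the risk-difference intervals are worth adding even if Fisher is kept.

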Recently a small randomized trial in cardiac surgery patients found a significant reduction in postoperative delirium (31% to 3%) when sub-anaesthetic doses of ketamine (0.5mg/kg) were given upon induction [13]. The same group further published data for improved postoperative cognitive function with ketamine in cardiac patients [13]. A follow up randomized prospective study in cardiothoracic patients looking at ketamine and delirium is currently recruiting (PODCAST).

Ketamine's benefits are thought to be based on its NMDA antagonism, HCN1 inhibitory effects and its anti-inflammatory properties [14]. Multiple studies have shown decreased post-operative pain with decreased post-operative opioid use when ketamine was administered during the surgery [15]. Interestingly a recent study showed that a single dose of ketamine had a prolonged two week lasting effect on patients with refractory depression [16].

Ketamine is a drug that has been in use for more than half a century, is inexpensive and has a wide margin of safety.

We are proposing a prospective randomized placebo controlled study to elucidate the effects of ketamine on postoperative delirium in the head and neck cancer population receiving “flaps”, administered peri-operatively.

4. Objectives:

Primary Aim:

Optimize our intraoperative treatment protocol for head and neck cancer patients to reduce the incidence of delirium and associated postoperative cognitive dysfunction. The hypothesis is that ketamine decreases delirium postoperatively in this high risk surgical patient population.

Secondary Aims:

1. Determine the dose response relationship for intraoperative ketamine and delirium reduction. Our hypothesis is that higher dose ketamine will lead to a more profound reduction in postoperative delirium.
2. Determine if a single dose of ketamine will reduce post-operative pain and opioid requirements. Our hypothesis is that the higher dose of ketamine will lead to a more profound decrease in objective pain scores.
3. Determine if raw EEG data can predict postoperative delirium during general anesthesia. Our hypothesis is that EEG patterns will correlate with incidence of post-operative delirium.
4. Evaluate length of ICU and length of hospital stay (done by medical chart review). Our hypothesis is that ketamine administration will not increase ICU/hospital stay.

5. Innovation, Impact & Leverage.

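### The trial is sized on both ketamine arms combined, but the primary analysis runs two separate dose-versus-placebo tests and does not say whether one or both must succeed

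*Combined protocol and SAP*

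**What the plan says.** Section 4 (Objectives, Primary Aim) gives one hypothesis and names no dose: "The hypothesis is that ketamine decreases delirium postoperatively in this high risk surgical patient population". A dose-response relationship is listed separately as the first secondary aim.

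Section 10a (Sample size) plans for 20 completed patients in each of three groups and claims "85% statistical power under significant level of 0.05". The effect assumed is a "delirium incidence rate drop at least 30% (placebo) to 5% (two treatment arms combined"). The test is described as "by one-sized Mantel Haenszel test", where the adjective is evidently meant to be one-sided.

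Section 10b (Data analysis) answers the primary aim differently. It gives incidence with a 95% confidence interval in each group, and then the groups are "compared between each ketamine treated group with placebo group through Fisher's exact test". The combined comparison does not appear in 10b. Under secondary aims, "the dose response effect of ketamine on delirium reduction will be tested by Cochran-Armitage trend test".

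Neither section gives the alpha or sidedness of the Fisher tests, or says how their two results together answer the single hypothesis.

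**The concern.** One hypothesis is put to two tests of equal rank, and the test that justified the sample size is not among them. If one dose is significant and the other is not, the plan does not say whether its hypothesis is supported. The same gap opens if neither dose reaches significance but the combined comparison would. Someone would then have to choose the rule after seeing the data, and the same results could be reported as positive or negative without departing from the protocol's words.

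This is a different matter from the power of each test. If each Fisher test were amply powered, mixed results would be rarer, but the plan would still not say what they mean.

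**Working it through.** **Inputs.** From section 10a: 20 completed per arm, placebo rate 30%, combined ketamine rate 5%, alpha 0.05, one-sided Mantel-Haenszel test, 85% power. Assumed: 5% in each ketamine arm, because the plan gives no per-dose rates. Also assumed: 0.05 for each Fisher test, shown one-sided and two-sided because 10b states neither.

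**Step 1: reproduce the plan's figure.** With a events on placebo (n = 20), m events in all and N = 60, the statistic is z = (a − 20m/60) / √V, where V = 20·40·m·(60 − m) / (60²·59). Reject when z > 1.645. Summing binomial probabilities over all outcomes at 30% (n = 20) and 5% (n = 40) gives **84.8%**, which matches 85%. The stated power therefore belongs to the combined comparison without continuity correction. Fisher's exact test on the combined arms would have 73.7% (one-sided) or 73.0% (two-sided).

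**Step 2: the two tests in 10b.** All 21³ outcomes for three arms of 20 were enumerated at 30% / 5% / 5%. The tests share a placebo arm, so the joint probability is computed directly. With P the probability for each test and B the probability that both are significant, at least one has probability 2P − B and exactly one has 2P − 2B.

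| | One-sided | Two-sided |
|---|---|---|
| Each test (P) | 54.4% | 44.6% |
| Both (B) | 42.5% | 30.1% |
| At least one | 66.3% | 59.0% |
| Exactly one | **23.9%** | **28.9%** |
| Combined test significant, neither dose | 19% | 26% |

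For example, one-sided, exactly one: 2 × 0.5439 − 2 × 0.4245 = 0.239. The combined test is the one-sided Mantel-Haenszel test in both columns.

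**Step 3: sensitivity.** Keeping the combined rate at 5% but splitting it 7% / 3% gives exactly one significant in 27.2% / 32.8% of trials. Splitting it 7.5% / 2.5% gives 29.0% / 35.0%. With 28 per arm (about 85 enrolled, divided by three), at 5% in each ketamine arm, it is 23.3% / 25.6%.

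**Step 4: two data sets.**

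- 6/20 placebo, 1/20 and 1/20 ketamine, exactly the planning rates. One-sided Fisher for each dose: [C(20,6)·C(20,1) + C(20,7)] / C(40,7) = 852,720 / 18,643,560 = 0.046. Two-sided it is twice that, 0.091. Combined: m = 8, 20m/60 = 2.667, V = 1.567, z = 3.333 / 1.252 = 2.66, one-sided p = 0.004. Two-sided Fisher fails at both doses while the sized test succeeds clearly.
- 7/20, 1/20 and 2/20. Two-sided Fisher gives 0.044 for one dose and 0.127 for the other.

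**Step 5: type I error at 20 per arm.** The chance that at least one Fisher test is significant, maximised over common null rates, is 4.9% one-sided and 4.7% two-sided. At a common rate of 30%, choosing afterwards among every delirium test named in section 10 (two Fisher, combined, trend) gives 8.0% if all are one-sided. If Fisher and trend are two-sided and only results favouring ketamine count, it is 5.9%. Without the trend test, the two Fisher tests plus the combined test give 6.6%, all one-sided.

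**The case against.** The trial is labelled a pilot. The first output in 10b is incidence with confidence intervals, and the primary aim is worded as optimising a treatment protocol. A mixed result could be reported dose by dose, and nothing in the document ties an action to a significant result. That lowers the stakes. But the plan still states a directional hypothesis, an alpha, a power and formal tests, so it should say which result answers the hypothesis.

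It can also be said that 24% to 29% is not an error rate, since two tests with about 54% or 45% power will often disagree. That is correct. The figure shows how often the missing rule would matter, not how often a false claim would be made.

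Three stronger readings are tempting, and the documents do not support them:

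- A reader might infer that two unadjusted primary tests inflate type I error. At 20 per arm they do not, because Fisher's test is conservative at that size.
- A reader might then infer that an either-dose rule never needs an alpha adjustment. That holds only at exactly 20/20/20. The maximum is 5.8% / 6.1% (one-sided / two-sided) at 25 per arm, and 6.1% / 5.9% with 22 on placebo and 19 on each dose. The document mentions at least 60, about 85 and up to 100 patients, with replacement of some, so final arm sizes are not fixed at 20.
- A reader might infer that the plan ranks nothing. It does place the trend test under the secondary aims. The 8.0% figure therefore requires overriding that label and also treating the sample-size test as an analysis option. Counting significant results in which ketamine looks worse would raise the figure further, but such results cannot support the hypothesis.

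**Conclusion.** The point holds as a mismatch between the test that is sized and the tests that decide, together with a missing success rule. Under the planning rates the chance of a positive trial runs from 30% (both doses, two-sided) to 85% (combined test), depending on a rule the plan does not state. This rests on 20 per arm, 30% on placebo, an assumed 5% in each ketamine arm and 0.05 per test. Unequal dose effects, which the plan's own secondary hypothesis expects, make disagreement more frequent in the splits tried. The harm is an undefined success criterion. Type I error is a lesser matter and arises only if the deciding test is chosen afterwards. It should be corrected, but it does not invalidate the design.

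**What to change.** Amend section 10b before unblinding:

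1. Make the combined ketamine arms versus placebo comparison, as sized in 10a, the single deciding test of the primary hypothesis, at the alpha and sidedness stated there.
2. If it is significant, test each dose against placebo by Fisher's exact test at the same alpha and sidedness, in a fixed order written in advance, stopping at the first failure.
3. Keep the trend test secondary and supportive, and say that it cannot establish the primary claim.

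This takes a few sentences and no extra patients or data, and the 85% in 10a then describes the test that decides. The cost is dilution if only one dose works. With 30% in placebo and in one ketamine arm and 5% in the other, the combined test has 28% power against 54% for a direct one-sided Fisher test of the effective dose. Under the fixed order, a dose placed second is also not tested if the first fails. The sponsor should accept these costs knowingly when writing the rule.

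### Secondary Aim 1: a significant trend across placebo, 0.5 and 1.0 mg/kg does not show that 1.0 reduces delirium more than 0.5, and no between-dose estimate is planned

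*Combined protocol and SAP*

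**What the plan says.** Section 4 states Secondary Aim 1 as "Determine the dose response relationship for intraoperative ketamine and delirium reduction", and adds: "Our hypothesis is that higher dose ketamine will lead to a more profound reduction in postoperative delirium". Section 10b assigns one analysis to this aim: "the dose response effect of ketamine on delirium reduction will be tested by Cochran-Armitage trend test". It does not state the scores or whether the test is one- or two-sided.

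For delirium, Section 10b otherwise plans two things. First, "the incidence of delirium will be calculated in each of three randomized group with 95% confidence interval (CI"). Second, the incidence is to be "compared between each ketamine treated group with placebo group through Fisher's exact test". The three-group comparisons that follow concern other outcomes (pain, MMSE, EEG, length of stay, narcotics). No difference, ratio or interval comparing 1.0 with 0.5 mg/kg is planned for delirium.

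Section 10a gives one ketamine rate for both doses: a drop from "30% (placebo) to 5% (two treatment arms combined"). It offers no dose-specific rates.

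**The concern.** The hypothesis compares two active doses, but the test runs over three groups, one of which is placebo. If ketamine works equally well at both doses, placebo still lies above the two ketamine arms and the trend test tends to reject. The plan does not say what a significant trend may be taken to show, so such a result could be reported as confirming that the higher dose does better.

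A plateau is plausible on the plan's own inputs. The sample size uses 5% for the two doses together, and Section 3 cites a fall from 31% to 3% with 0.5 mg/kg in cardiac surgery. If rates like these hold at the lower dose, little room remains for a further reduction.

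At stake is how the pilot's dose-response result is read. The primary comparison is not affected.

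**Working it through.** **Inputs.** 20 completers per arm, placebo rate 30%, ketamine rate 5% for the doses combined, alpha 0.05 (all Section 10a); doses 0, 0.5 and 1.0 mg/kg (Section 6). Assumed: 5% in each ketamine arm separately, scores 0/0.5/1, and a two-sided test as the main case. Scores 0/1/2 give the same test because the doses are equally spaced.

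**The plan's own figure.** The 85% power for 30% versus 5% (20 versus 40 patients) reproduces: exact binomial enumeration of the uncorrected one-sided Mantel-Haenszel test gives 84.8%.

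**Form of the trend statistic.** Let P, L and H be the delirium counts in the placebo, 0.5 and 1.0 mg/kg arms, and p = (P + L + H)/60.

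- Numerator: T = 0.5L + H − 0.5(P + L + H) = 0.5(H − P). L cancels.
- Variance: p(1 − p) × [20 × (0 + 0.25 + 1) − 30²/60] = p(1 − p) × (25 − 15) = 10p(1 − p). L enters only here, through the pooled rate.

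**Two example tables.**

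| P, L, H (of 20) | p | T | z | p-value (exact) | 1.0 minus 0.5, Newcombe 95% CI |
|---|---|---|---|---|---|
| 6, 1, 1 | 8/60 | −2.5 | −2.5/√1.156 = −2.33 | 0.020 (0.034) | 0 points, −19 to +19 |
| 7, 0, 2 | 9/60 | −2.5 | −2.5/√1.275 = −2.21 | 0.027 (0.045) | +10 points, −8 to +30 |

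The first is significant with identical dose results. The second is significant with more cases at the higher dose.

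**How often.** All 21³ tables were enumerated, each weighted by its binomial probability.

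At 30%/5%/5%, the trend is significant for benefit in:

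- 68.4% (asymptotic, two-sided)
- 77.9% (asymptotic, one-sided)
- 58.4% (exact, two-sided)
- 68.7% (exact, one-sided)

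This is power against no ketamine effect, not a false-positive rate. At 30%/30%/30% the asymptotic two-sided test rejects in 5.4% of trials, both directions together.

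Share of all trials with a significant benefit trend (asymptotic, two-sided) and H at or above L:

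| True rates: placebo, 0.5, 1.0 mg/kg | H ≥ L and significant |
|---|---|
| 30, 5, 5 | 41.6% (24.7% ties, 17.0% H above L) |
| 30, 7.5, 2.5 (assumed) | 27.8% |
| 30, 10, 0 (assumed) | 11.7% |

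In the first row these are 0.416/0.684, or about 61%, of the significant results.

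**What a direct estimate would do.** The Newcombe 95% CI for 1.0 minus 0.5 mg/kg lies wholly below zero in 0.1% of trials at 5% versus 5%. With 5% at the higher dose and an assumed 15% at the lower, the figure is about 9%; with 20% at the lower, about 21%.

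**The case against.** Cochran-Armitage is a standard test for a binary outcome over ordered doses, and the aim as worded asks for a dose-response relationship. The hypothesis can be read as an ordered response that includes zero dose, and nowhere does the plan say that a significant trend will be taken as proof that 1.0 beats 0.5 mg/kg.

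The planned outputs would also expose many awkward cases. For 7/20, 0/20, 2/20 the planned Fisher tests against placebo give p = 0.008 at 0.5 mg/kg and p = 0.127 at 1.0 mg/kg, beside incidences of 0% and 10%. A reader could derive the difference from the counts.

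The size depends on the scenario. Most of the 42% is ties, and about 13 of the 17 points with H above L are differences of one case. At an assumed 30%/15%/5% the share falls to about 10%. The exact cancellation of L needs equal arms. Finally, the added interval will rarely settle anything with 20 per arm.

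Most of this stands as a limit on severity. It does not remove the mismatch. Two separate per-arm intervals and two placebo contrasts do not give an interval for the difference between doses, and the plan has no rule to stop the trend p-value standing in for it. That the interval will be wide is a reason to report it, so that the uncertainty is visible.

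**Conclusion.** The concern holds. The trend test is a sound test of whether delirium is associated with dose when placebo is included. It cannot separate a plateau from a graded response, and the plan contains no estimate that addresses the difference between the two doses.

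Under 30%/5%/5% with 20 per arm, a two-sided trend is significant in 68% of trials with no dose difference. In 42% of all trials it is significant with the observed high-dose count no better than the low-dose count. These figures rest on the assumed equal split of the combined 5% rate, equal arms and asymptotic p-values; the 42% shrinks as the true doses diverge.

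This is a secondary aim of a pilot and the remedy is cheap, so the change should be made, but it does not threaten the trial's main result.

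**What to change.** In Section 10b:

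1. Keep the trend test as evidence of an overall ketamine dose-response against no effect, and state its scores and sidedness.
2. Add the 1.0 minus 0.5 mg/kg risk difference in delirium with a 95% CI, for example by Newcombe's method.
3. State that any claim of a larger reduction at the higher dose will rest on that interval and not on the trend p-value.
4. State that with 20 per arm this comparison is estimation only, with an interval of about ±19 points at 1/20 versus 1/20.

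The cost is one derived estimate from data already collected and two or three sentences. No extra patients or powered test are needed. The downside is that the protocol would then admit openly that the pilot is unlikely to separate the doses.
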